##### I 02. Prior anticancer therapy

Have failed no more than 2 systemic anti-cancer regimens (a platinum-containing regimen, AND an anti-PD-1/PD-L1 based regimen, administered either sequentially or concurrently, unless these regimens are already given in locally advanced disease) in R/M disease:

- One previous anti-PD-1/PDL1 based regimen (may include chemotherapy agents as part of the regimen) failure defined as **disease progressed (when participants are still receiving) but after documented benefit, on an anti-PD1/PDL-1 based regimen** per RECIST 1.1. **Documentation of benefit** defined as stable disease [SD] at  $\geq 1$  radiographic imaging scan, CR, or PR from anti-PD1/PDL-1 based regimen. An anti PD-1/PD-L1 containing regimen is defined as either an anti PD-1/PD-L1 monotherapy, or an anti-PD-1/PD-L1 agent administered in the same cycle as another systemic anti-cancer therapy. If an anti-PD-1/PDL-1 agent was used beyond initial radiological progression (without change the anti-PD-1/PDL-1 agent used before progressive disease), it's still considered as the same regimen. The site's study team must have reviewed previous tumor assessments (including screening tumor imaging) to determine that radiographic progression has occurred per RECIST 1.1 following initiation of the anti PD-1/PD-L1 containing regimen.

AND

- One previous platinum-containing regimen failure defined as either disease progression on or after treatment with a platinum-containing regimen.

**5.2 EXCLUSION CRITERIA**

Please refer to master protocol.

**5.3 LIFESTYLE CONSIDERATIONS**

Please refer to the master protocol.

**5.4 SCREEN FAILURES**

Please refer to the master protocol.

**5.5 CRITERIA FOR TEMPORARILY DELAYING  
(ENROLLMENT/RANDOMIZATION/ADMINISTRATION OF STUDY INTERVENTION  
ADMINISTRATION)**

Please refer to the master protocol.

## 6 STUDY INTERVENTION(S) AND CONCOMITANT THERAPY

### 6.1 STUDY INTERVENTION(S) ADMINISTERED

Please refer to the master protocol.

The maximum number of cycles allowed in this Cohort B1 substudy is 35 cycles.

Dosing sequence:

#### 6.1.1 Investigational medicinal product

Investigational medicinal product (IMP) is defined as SAR444245, and pembrolizumab administered as described in [Section 4.1](#). Details of each IMP component to be administered are shown in [Table 1](#).

Preparation and administration of IMP are detailed in the pharmacy manual. Hydration is required for SAR444245 infusions. Details are provided in Section 6.1.3 of the master protocol.

**Table 1 - Overview of IMP administered**

| Intervention name                   | SAR444245           | Pembrolizumab  |
|-------------------------------------|---------------------|--|
| Type                                | See master protocol | Biologic   |
| Dose formulation                    | See master protocol | Solution for infusion  |
| Unit dose strength(s)               | See master protocol | 25 mg/mL   |
| Dosage level(s) a        | 24 µg/kg Q3W        | 200 mg Q3W   |
| Route of administration             | See master protocol | IV infusion  |
| Use                                 | See master protocol | Treatment of cancer (combination)  |
| IMP or NIMP                         | IMP                 | IMP  |
| Packaging and labeling              | See master protocol | Supplied in single-dose vials containing 100 mg/4 mL pembrolizumab labelled with a multilingual booklet. 1 vial per treatment box. |
| Current/Former name(s) or alias(es) | NA                  | Keytruda   |

a The total dose will be calculated based on the weight on the day of the infusion or the most recent weight assuming it was assessed in a reasonable time frame according to Investigator assessment. Study sites should make every effort to measure body weight as close to the infusion day as possible considering the variability of local process from site to site. If the infusion is prepared with the most recent weight assessed in a reasonable time frame, the participant must still be weighed on D1 of each cycle, and the weight recorded in the e-CRF. Study sites should make every effort to target infusion timing to be as close to 30 minutes as possible. However, given the variability of infusion pumps from site to site, a window between -5 minutes and +10 minutes is permitted (ie, infusion time is 30 minutes -5 min/+10 min).

### **6.1.2 Non-investigational medicinal product**

Please refer to the master protocol.

### **6.1.3 Hydration guidelines for SAR444245 administration**

Please refer to the master protocol.

### **6.1.4 Readiness for treatment of severe cytokine release syndrome**

Please refer to the master protocol.

## **6.2 PREPARATION/HANDLING/STORAGE/ACCOUNTABILITY**

Please refer to the master protocol.

## **6.3 MEASURES TO MINIMIZE BIAS: RANDOMIZATION AND BLINDING**

Not applicable.

## **6.4 STUDY INTERVENTION COMPLIANCE**

Please refer to the master protocol.

## **6.5 DOSE MODIFICATION**

### **6.5.1 General rules**

Dose modifications for SAR444245 are permitted according to the guidelines described in this section. Pembrolizumab dose reductions are not permitted. Pembrolizumab treatment may be interrupted or discontinued due to toxicity.

Dose modifications different from those stated in the protocol should only be made in consultation with the Sponsor, unless required for immediate participant safety.

**Cycle delay** (ie, Day 1 should be delayed for all IMPs) is permitted in case of treatment-emergent adverse event (TEAE). Dose modification will be made according to the worst grade of toxicity observed within a cycle. If a participant experiences several toxicities and there are conflicting recommendations, the most conservative recommended dose adjustment should be followed. Once a dose has been decreased, intra-patient re-escalation back to the previous dose level is not permitted.

Administration of the study treatment will be discontinued in the event of a TEAE that persists despite appropriate dose modifications or any other TEAE that, in the opinion of the Investigator, warrants discontinuation.

If a toxicity leads to SAR444245 discontinuation, pembrolizumab must be discontinued unless the TEAE leading to permanent IMP discontinuation is clearly attributable only to SAR444245, and patients have clinical benefit as determined by the treating physician.

Participants who continue pembrolizumab in this scenario are informed as part of the initial consent process that pembrolizumab monotherapy is not a standard of care. In this case it is partial permanent discontinuation and the end of treatment (EOT) assessment will be 30 days after the date of the last administration of the remaining IMP. When all IMP components are permanently discontinued it is full permanent discontinuation.

All changes to study treatment administration must be recorded in the electronic case report form (e-CRF).

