### **6.5 DOSE MODIFICATION**

#### **6.5.1 General rules**

Dose modifications for SAR444245 is permitted according to the guidelines described in this section. Pembrolizumab dose reductions are not permitted. Pembrolizumab treatment may be interrupted or discontinued due to toxicity. Dose modifications for cetuximab are permitted, and modification of dose levels in case of dose reduction is described in [Table 5](#).

Dose modifications different from those stated in the protocol should only be made in consultation with the Sponsor, unless required for immediate participant safety.

**Cycle delay** (ie, Day 1 should be delayed for all IMPs) or **dose omission** (ie, omission of any component of the IMP within a cycle) are permitted in case of treatment-emergent adverse event (TEAE). Dose modification will be made according to the worst grade of toxicity observed within a cycle. If a participant experiences several toxicities and there are conflicting recommendations, the most conservative recommended dose adjustment should be followed. Once a dose has been decreased, intra-patient re-escalation back to the previous dose level is not permitted.

Administration of the study treatment will be discontinued in the event of a TEAE that persists despite appropriate dose modifications or any other TEAE that, in the opinion of the Investigator, warrants discontinuation.

If any of the IMP components is permanently discontinued, the other IMP component can be continued until disease progression or other criteria as detailed in Section 7.1.1 of the master protocol are met. In this case it is partial permanent discontinuation and the end-of-treatment (EOT) assessment will be 30 days after the date of the last administration of the remaining IMP(s). When all IMP components are permanently discontinued it is full permanent discontinuation.

All changes to study treatment administration must be recorded in the electronic case report form (e-CRF).

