### 6.5.2 Cycle delay

The treatment window is  $\pm 3$  days for each of the Q3W administrations. A cycle is deemed to have been delayed if the treatment is administered  $\geq 4$  days beyond the theoretical day of Q3W IMP administration. The participant may receive the next dose after recovery from the toxicity as described in [Section 6.5.3](#). After cycle delayed, such participants may be considered for treatment resumption once the toxicity resolves or improves to Grade 1 or baseline.

Participants may have cycle delay, if toxicity occurs and the participant does not recover according to following rules:

- For Q3W IMP administration: If toxicity occurs and the participant does not recover on the day of planned administration, the cycle will be delayed; restart of study IMPs could occur only on the initiation of the subsequent cycle.
- In case of cycle delay for the recovery of toxicity, the following rules should be followed for restart or discontinuation of the treatment:
  - In case of a cycle delay up to 14 days, it is per Investigator's decision to restart the study treatment.
  - After a cycle delay of  $>14$  days and  $\leq 84$  days, it is per Investigator's decision to restart the study treatment, if a clear benefit from treatment is observed and after consultation with the Sponsor.
  - The study treatment must be permanently discontinued if the cycle delay is longer than 84 days.
- Cycle may be delayed for situations other than TEAEs such as medical/surgical events or logistical reasons not related to study therapy. Participants should be placed back on study therapy within 21 days of the scheduled delay, unless otherwise discussed with the Sponsor (for example for national or regional emergencies). The reason for this delay should be documented in the participant's study record.

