**Table 3 - SAR444245 Infusion-related reaction dose modification and treatment guidelines**

| NCI CTCAE Grade   | Treatment  |
|---|--|
| Grade 1
Mild transient reaction; infusion interruption not indicated; intervention not indicated  | 
If IRR happens during infusion, continuation of SAR444245a infusion is per Investigator's judgment following close direct monitoring of the participant's clinical status.
 
SAR444245 infusion may be interrupted at any time if deemed necessary.
 
If interrupted, IRR will be classified as Grade 2 as per NCI-CTCAE definition.
 
If IRR happens after completion of infusion, increase monitoring of vital signs as medically indicated until the participant is deemed medically stable in the opinion of the investigator.
  |
| Grade 2
Therapy or infusion interruption indicated but responds promptly to symptomatic treatment (eg, antihistamines, NSAIDs, narcotics, IV fluids); prophylactic medications indicated for ≤24 hrs. | 
Interrupt SAR444245 infusion.
 
If symptoms resolve within 1 hour of interrupting drug infusion, the infusion may be restarted at 50% of the original infusion rate. Otherwise dosing will be held until symptoms resolve and the participant will be premedicated for the next scheduled dose according to Section 6.1.2.1 of the master protocol.
 
Give the next infusion at half the infusion rate.
 
During or after completion of infusion, additional appropriate medical therapy may include but not limited to IV fluids, antihistamines, NSAIDs, acetaminophen, narcotics.
 
Increase monitoring of vital signs will be as medically indicated until the participant recovers.
 |

| NCI CTCAE Grade   | Treatment   |
|---|---|
| Grade 3
Prolonged (ie, not rapidly responsive to symptomatic medication and/or brief interruption of infusion); recurrence of symptoms following initial improvement; hospitalization indicated for other clinical sequelae | Permanently discontinue SAR444245. The participant can continue treatment with the other anti-cancer therapy in combination
During or after completion of infusion, additional appropriate medical therapy may include but is not limited to epinephrine b , IV fluids, antihistamines, NSAIDs, acetaminophen, narcotics, oxygen, vasopressors, corticosteroids.
Increase monitoring of vital signs as medically indicated until the participant recovers. |

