#### 6.5.4.4 Immune-related adverse events

AEs associated with pembrolizumab exposure may represent an immunologic etiology. These irAEs may occur shortly after the first dose or several months after the last dose of pembrolizumab treatment and may affect more than one body system simultaneously. Immune-related AEs (irAEs) are thought to be caused by unrestrained cellular immune responses directed at the normal host tissues. Therefore, early recognition and initiation of treatment is critical to reduce complications. Based on existing pembrolizumab clinical study data, most irAEs were reversible and could be managed with interruptions of pembrolizumab, administration of corticosteroids and/or other supportive care.

Investigators must be extremely vigilant and be ready to intervene early in the management of irAEs because the onset of symptoms of irAEs (eg, pneumonitis) may be subtle. For suspected irAEs, adequate evaluation should be performed to confirm etiology or exclude neoplastic, infectious, metabolic, toxin, or other etiologic causes. Additional procedures or tests such as bronchoscopy, endoscopy, skin biopsy may be included as part of the evaluation. Based on the severity of irAEs, withhold or permanently discontinue pembrolizumab and/or SAR444245 and administer corticosteroids.

SAR444245 may increase the incidence and severity of these events.

Dose modification and toxicity management guidelines for irAEs are provided in [Table 5](#). Of note, if the AE is considered immune-related, both drugs in the combination should be held according to recommended dose modifications. If a participant experiences several irAEs, the most conservative recommendation should be followed.

The CTCAE V5.0 must be used to grade the severity of AEs.

When pembrolizumab can be restarted, it should be administered at the initial planned dose and schedule as no modification is allowed:

- If the toxicity does not resolve or the criteria for resuming treatment are not met, the participant must be discontinued from all study drugs.
- If the toxicities do resolve and conditions are aligned with what is defined in [Table 5](#), the combination of SAR444245 and pembrolizumab may be restarted at the discretion of the investigator. In these cases where the toxicity is attributed to the combination or to SAR444245 alone, re-initiation of pembrolizumab as a monotherapy may be considered after communication with the Sponsor.

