**Table 5 - Dose modification and toxicity management guidelines for immune-related AEs associated with pembrolizumab and SAR444245**

General instructions:

1. Treat severe and life-threatening irAEs should be treated with IV corticosteroids followed by oral steroids. Begin other immunosuppressive treatment should begin if the irAEs are not controlled by corticosteroids.
2. Pembrolizumab and SAR444245 must be permanently discontinued if the irAE does not resolve or the corticosteroid dose is not  $\leq 10$  mg/day within 12 weeks of the last pembrolizumab treatment.
3. Begin the corticosteroid taper should begin when the irAE is  $\leq$  Grade 1 and continue at least 4 weeks.
4. If pembrolizumab and SAR444245 have been withheld, pembrolizumab and SAR444245 may be resumed after the irAE decreased to  $\leq$  Grade 1 after corticosteroid taper.

| irAEs       | Toxicity grade (CTCAE V5.0)     | Action with pembrolizumab and SAR444245 | Corticosteroid and/or other therapies   | Monitoring and follow-up   |
|-------------|---------------------------------|---|---|--|
| Pneumonitis | Grade 2                         | Withhold a                   | Administer corticosteroids (initial dose of 1 to 2 mg/kg prednisone or equivalent) followed by taper.
Add prophylactic antibiotics for opportunistic infections. | Monitor participants for signs and symptoms of pneumonitis.
Evaluate participants with suspected pneumonitis with radiographic imaging and initiate corticosteroid treatment. |
|             | Recurrent Grade 2, Grade 3 or 4 | Permanently discontinue b    |   |  |

| irAEs  | Toxicity grade (CTCAE V5.0)   | Action with pembrolizumab and SAR444245                          | Corticosteroid and/or other therapies  | Monitoring and follow-up   |
|--|---|--|--|--|

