|   | Recurrent Grade 3 or Grade 4 | Permanently discontinue b                                 |   |   |

a SAR444245 to be withheld plus pembrolizumab to be withheld corresponds to "cycle delay".

b Permanently discontinuation of full study treatment.

c AST/ALT: >3.0 to 5.0 x ULN if baseline normal; >3.0 to 5.0 x baseline, if baseline abnormal; bilirubin:>1.5 to 3.0 x ULN if baseline normal; >1.5 to 3.0 x baseline if baseline abnormal.

d AST/ALT: >5.0 to 20.0 x ULN, if baseline normal; >5.0 to 20.0 x baseline, if baseline abnormal; bilirubin:>3.0 to 10.0 x ULN if baseline normal; >3.0 to 10.0 x baseline if baseline abnormal.

e AST/ALT: >20.0 x ULN, if baseline normal; >20.0 x baseline, if baseline abnormal; bilirubin: >10.0 x ULN if baseline normal; >10.0 x baseline if baseline abnormal.

f The decision to withhold or permanently discontinue pembrolizumab and SAR444245 is at the discretion of the investigator or treating physician. If control achieved or ≤Grade 2, pembrolizumab and SAR444245 may be resumed.

g Events that require discontinuation include but are not limited to: encephalitis and other clinically important irAEs (eg. vasculitis and sclerosing cholangitis).

AE(s)=adverse event(s); ALT= alanine aminotransferase; AST=aspartate aminotransferase; CTCAE=Common Terminology Criteria for Adverse Events; DRESS=Drug Rash with Eosinophilia and Systemic Symptom; GI=gastrointestinal; IO=immuno-oncology; ir=immune related; IV=intravenous; SJS=Stevens-Johnson Syndrome; T1DM=type 1 diabetes mellitus; TEN=Toxic Epidermal Necrolysis; ULN=upper limit of normal.

Note: Non-irAE will be managed as appropriate, following clinical practice recommendations.

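### In Cohort B1, an immune-related event that has resolved and is attributed to the combination bars pembrolizumab alone under Section 6.5.1 but permits it under Section 6.5.4.4

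*Protocol*

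**What the plan says.** All references are to Substudy 04 (Cohort B1) unless stated otherwise.

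Section 6.5.1 sets the general rule. If a toxicity leads to SAR444245 being discontinued, "pembrolizumab must be discontinued unless the TEAE leading to permanent IMP discontinuation is clearly attributable only to SAR444245, and patients have clinical benefit", with benefit judged by the treating physician. The same section acknowledges that pembrolizumab alone is not standard of care here. It says that participants who continue it in that scenario are told so during initial consent.

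Section 6.5.4.4 covers immune-related adverse events. Both drugs are held. If the event resolves and the Table 5 conditions are met, the investigator may restart the combination. For an event "attributed to the combination or to SAR444245 alone, re-initiation of pembrolizumab as a monotherapy may be considered after communication with the Sponsor".

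Actions by grade are set out in Table 5. General instruction 4 deals with events that led to a hold: "If pembrolizumab and SAR444245 have been withheld, pembrolizumab and SAR444245 may be resumed after the irAE decreased to" Grade 1 or lower, after steroid taper. Footnote b defines permanent discontinuation as "Permanently discontinuation of full study treatment".

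Section 6.5.2 adds a condition for restarts after a delay of more than 14 and up to 84 days: "if a clear benefit from treatment is observed and after consultation with the Sponsor".

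**The concern.** Section 6.5.1 is mandatory and does not exempt immune-related events. Section 6.5.4.4 permits what Section 6.5.1 forbids when the event is put down to the combination. The sections do not refer to each other on this point, so two sites could treat identical events differently and each cite the protocol.

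The population makes this matter. B1 enrols people whose "disease progressed (when participants are still receiving) but after documented benefit, on an anti-PD1/PDL-1 based regimen" (inclusion criterion I 02). Pembrolizumab alone therefore returns them to a drug class on which they have already progressed. Section 6.5.1 confines that to a toxicity clearly due only to SAR444245 with clinical benefit, and its consent statement is tied to that scenario. Section 6.5.4.4 opens a route outside it.

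**Working it through.** No stated figure is involved, so the check is a comparison of texts and a count of where the conflict can occur.

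**Step 1. Attribution.** Consider an immune-related event that was withheld and has resolved.
- Attributed only to SAR444245: both sections can allow pembrolizumab alone, Section 6.5.1 on condition of clinical benefit.
- Attributed to the combination: the attribution condition in Section 6.5.1 fails by definition, so pembrolizumab must stop. Section 6.5.4.4 says monotherapy may be considered. This is the conflict.

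**Step 2. Is Section 6.5.1 triggered?** It applies when a toxicity leads to SAR444245 discontinuation. For immune-related events Section 6.5.4.4 holds both drugs, and Section 6.5.1 defines a cycle delay as covering all study drugs. Restarting pembrolizumab as monotherapy because of that toxicity therefore means SAR444245 was dropped for it, and Section 6.5.1 applies.

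**Step 3. Does another clause settle it?**
- The most-conservative-recommendation clause in Section 6.5.1 covers several toxicities, and the one in Section 6.5.4.4 covers several immune-related events. Neither covers one event under two rules.
- The Sponsor-consultation clause in Section 6.5.1 concerns dose modifications that the protocol does not state. Here both rules are stated.
- Section 6.5.3 leaves resumption to investigator and Sponsor unless the protocol specifies otherwise, which Section 6.5.1 does.

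**Step 4. Where can it occur?** Table 5, counted by grade row:

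| Action | Rows | Conflict possible? |
|---|---|---|
| Withhold | 9 | Yes |
| Withhold or discontinue | 3 | Yes, if withheld |
| Permanent discontinuation (footnote b) | 8 | No, all treatment stops |
| Continue | 2 | No |
| Total | 22 | 9 + 3 = 12 |

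In each of the 12 rows three more conditions must hold: the event resolves, it is attributed to the combination, and SAR444245 is not restarted because of it. The count shows scope in the table. It is not an event rate, and the protocol gives none.

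**Step 5. Likely source of the wording (an inference).** The same sentence stands in Section 6.5.4.4 of Substudy 02 (Cohort A2). It fits there, because Section 6.5.1 of that substudy is permissive: "If any of the IMP components is permanently discontinued, the other IMP component can be continued until disease progression". B1 has a stricter Section 6.5.1 with the same sentence in Section 6.5.4.4.

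**The case against.** The best defence is that the sections address different branches: Section 6.5.1 a permanent stop, Section 6.5.4.4 a restart after a hold. A specific provision for immune-related events would then qualify the general rule. Section 6.5.3 calls the Section 6.5.4 text recommended guidelines and leaves the final decision to the investigator's judgment. Section 6.5.4.4 is also permissive and requires communication with the Sponsor, so a site would not act alone.

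Much of this limits the practical risk. It does not remove the conflict. A restart of one drug only, after both were held, is a discontinuation of the other. No precedence is stated, and general discretion does not tell an investigator which of two written rules is meant. It is true that B1 delays SAR444245 alone for other events (cytokine release syndrome, ICANS, vascular leak syndrome), so Step 2 holds for immune-related events and should not be extended to those.

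Three stronger readings are tempting but not supported.

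- **That Table 3 conflicts too.** For Grade 3 and 4 SAR444245 infusion reactions it says "Permanently discontinue SAR444245. The participant can continue treatment with the other anti-cancer therapy in combination". That table covers only reactions to SAR444245, which is consistent with the attribution condition. Its wording is permissive and does not cancel the benefit condition in Section 6.5.1.
- **That the absent benefit condition in Section 6.5.4.4 is a gap of equal weight.** Section 6.5.2 already asks for clear benefit after delays beyond 14 days, and Table 5 requires a steroid taper of at least 4 weeks. With the next dose due on Day 22, a 28-day taper starting on Day d ends no earlier than Day d + 28. That is a delay of d + 6 days, which exceeds 14 when d is above 8. What remains is mainly short holds.
- **That pembrolizumab alone is foreign to B1.** Section 6.5.1 itself accepts it, under stated conditions.

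**Conclusion.** The conflict is real and narrow. For a B1 participant whose immune-related event was withheld, has resolved, is attributed to the combination, and is the reason SAR444245 is not restarted, Section 6.5.1 requires pembrolizumab to stop. Section 6.5.4.4 allows it alone after communication with the Sponsor.

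A reader might infer that the contradiction affects every immune-related event, or that it biases the ORR or the decision to open the expansion phase. The documents support neither. It is excluded wherever footnote b stops full study treatment. No frequency is given for the events that remain, and no stated statistical figure changes.

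The point should be corrected because it concerns a treatment-stopping rule in participants who progressed on anti-PD-1/PD-L1 therapy. The conclusion rests on the substudy text alone. Section 7.1 defers to the master protocol, which is not in the material reviewed and might set an order of precedence. The two B1 sentences would still need to agree.

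**What to change.** In B1 Section 6.5.4.4, delete the reference to the combination from the sentence on restarting pembrolizumab alone, and make that sentence subject to the conditions of Section 6.5.1. The cross-reference also carries over the clinical-benefit condition, so no separate benefit wording is needed.

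Which rule is intended is the sponsor's clinical decision. If it is the permissive one, write an explicit exception for immune-related events into Section 6.5.1 and extend the consent statement to cover it.

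The first option edits one sentence at the next amendment and adds no procedures. The second edits Section 6.5.1 and the consent wording. Table 3 needs no change, and the sentence in Substudy 02 can stay.

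### Cohort B1: after toxicity attributed to the combination, Section 6.5.1 requires pembrolizumab to stop while Section 6.5.4.4 lets it be restarted alone

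*Protocol*

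**What the plan says.** All references are to substudy 04 (Cohort B1) unless stated.

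- **Population.** Inclusion criterion I 02 requires that "disease progressed (when participants are still receiving) but after documented benefit, on an anti-PD1/PDL-1 based regimen".
- **Section 6.5.1, General rules.** If toxicity leads to SAR444245 being discontinued, "pembrolizumab must be discontinued unless the TEAE leading to permanent IMP discontinuation is clearly attributable only to SAR444245, and patients have clinical benefit". The treating physician judges benefit. The same section says participants who go on in this way are told at consent that "pembrolizumab monotherapy is not a standard of care".
- **Section 6.5.4.4, Immune-related adverse events.** Where the toxicity has resolved and the conditions of Table 5 are met, the combination may be restarted. The section then adds: "In these cases where the toxicity is attributed to the combination or to SAR444245 alone, re-initiation of pembrolizumab as a monotherapy may be considered". Contact with the Sponsor must come first.
- **Table 3, SAR444245 infusion-related reactions, Grades 3 and 4.** "Permanently discontinue SAR444245. The participant can continue treatment with the other anti-cancer therapy in combination".
- **Section 6.5.2, Cycle delay.** Restart after a delay of more than 14 and up to 84 days needs clear benefit and Sponsor consultation. Restart after a shorter delay is left to the investigator.

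**The concern.** Section 6.5.1 is a mandatory stop with one exception, and both limbs of that exception must be met. An event attributed to the combination is, by definition, not attributable only to SAR444245, so the exception is closed. Section 6.5.4.4 opens the same door for immune-related events. A site following one section would breach the other.

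This matters for conduct more than for any calculation. Participants in B1 have progressed while receiving a drug of this class, and the protocol itself says pembrolizumab alone is not standard care for them. The consent disclosure in 6.5.1 is tied to the situation which that section describes. Which participants remain on pembrolizumab without SAR444245 could then depend on which section the site, or the Sponsor when contacted, applies.

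**Working it through.** No sample size, error rate or event count is involved, so the check is a comparison of the three texts, with two small timing calculations.

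| Condition | 6.5.1 | 6.5.4.4 (immune-related events) | Table 3 (SAR444245 infusion reaction, Grade 3-4) |
|---|---|---|---|
| Attribution | SAR444245 only, clearly | Combination, or SAR444245 alone | SAR444245, implied by the title |
| Clinical benefit | Required | Not stated | Not stated |
| Sponsor contact | Not stated | Required | Not stated |

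**Case A: immune-related event attributed to the combination, resolved, SAR444245 not resumed.** Under 6.5.1 the attribution condition fails, so pembrolizumab must stop whether or not there is benefit. Under 6.5.4.4 it may be restarted alone after Sponsor contact. The two instructions are opposite.

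**Case B: immune-related event attributed to SAR444245 alone, no benefit judged.** Section 6.5.1 says stop, and 6.5.4.4 states no benefit condition. Section 6.5.2 narrows this gap. Table 5 equates withholding both drugs with a cycle delay. Where corticosteroids are used, it has the taper start at Grade 1 or below, last at least 4 weeks, and precede resumption. Let x be the days from the last dose to Grade 1 or below. The earliest restart is then x + 28 days after that dose, against a planned 21, so the delay is at least x + 28 - 21 = x + 7 days. This exceeds 14 days when x > 7, and the clear-benefit condition of 6.5.2 then applies. Shorter delays and events managed without steroids may escape it. In no case does 6.5.2 address attribution, so it leaves Case A untouched.

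**Case C: Grade 3 or 4 SAR444245 infusion reaction, no benefit judged.** Section 6.5.1 says stop. Table 3 says the other therapy can continue. With 21-day cycles, the first three infusions fall on days 1, 1 + 21 = 22 and 22 + 21 = 43. The first scheduled scan is at 63 ± 7 days, so no earlier than 56 days after the first dose. A reaction at any of those infusions comes before scheduled imaging evidence of benefit.

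**Case D: event clearly attributable only to SAR444245, with benefit.** Section 6.5.1 and whichever of the other two texts covers the event both allow pembrolizumab to go on. 6.5.4.4 adds Sponsor contact.

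**Is there a tie-breaker?** The instruction in 6.5.1 to follow the most conservative adjustment covers a participant with several toxicities, and the parallel sentence in 6.5.4.4 covers several immune-related events. Neither covers one event under two rules. The stop in 6.5.1 carries no exception for provisions elsewhere, although 6.5.3 uses such wording for delays. Table 5 footnote b ends all study treatment for listed grades, which limits when 6.5.4.4 can be used but says nothing about attribution.

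**A plausible source.** The Table 3 wording also stands in the matching tables of Cohorts A2 and B2, and the 6.5.4.4 sentence also stands in A2. The general rules of A2 and B2 let the other component continue, so the wording fits there. Of the three substudies at hand, only B1 has the restrictive general rule. That the text was carried across is an inference, and the contradiction does not depend on it.

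**The case against.** Much can be said for a narrower view. Table 3 and 6.5.4.4 are permissive and sit below a general rule, so a specific permission can be read as subject to a general prohibition. For Table 3 this stands. Its title already ties the event to SAR444245, and the amendment log gives that as the reason for dropping an explicit attribution phrase. Only the benefit condition is missing, and a cross-reference would cure it.

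For 6.5.4.4 the reading does not work. If that sentence is subject to 6.5.1, its words about the combination have no effect. Sponsor contact is a real safeguard and makes site-to-site variation less likely. Section 6.5.1 also allows departures from the stated dose modifications in consultation with the Sponsor. But that allowance presupposes one stated rule to depart from, and here there are two. Section 6.5.3 leaves the final decision to the investigator's judgement, which does not turn a mandatory stop into an option.

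Several stronger readings are tempting, and the documents do not support them:

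- A reader might infer three mutually incompatible rules. Table 3 and 6.5.4.4 cover different events, so each differs from 6.5.1 and not from the other.
- A reader might infer that benefit cannot be shown before week 9. Benefit is the treating physician's judgement, and earlier imaging is allowed when clinically indicated. It is hard to establish early, but not excluded.
- A reader might infer that 96 participants are affected. That is the planned cohort, 40 + 56, and the 56 are enrolled only if the sponsor opens the expansion.
- A reader might infer that the consent form is wrong. Consent pages are not shown, and no misalignment is visible.

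**Conclusion.** The contradiction between 6.5.1 and 6.5.4.4 on attribution is real and lies in current text. For an immune-related event attributed to the combination, with SAR444245 not resumed, one section requires pembrolizumab to stop and the other lets it restart. The missing benefit condition in 6.5.4.4 is a lesser gap, partly covered by 6.5.2. The Table 3 point is milder still.

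The size cannot be given. The conflict bites only when toxicity ends SAR444245 and pembrolizumab alone is then considered, and the documents offer no rate for that. A reader might infer that the response analysis is altered. The populations and analyses are in the master protocol, which is not shown, and no figure in the substudy depends on this point.

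The conclusion assumes that the master protocol, to which Section 7.1 refers for discontinuation of study intervention, has no rule that decides the matter. Section 6.5.1 of B1 points to none for this decision. The documents do not show which rule is intended, and this review takes no position on which is clinically right.

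**What to change.** In the next substudy 04 amendment, reconcile 6.5.1 and 6.5.4.4 into one set of conditions for giving pembrolizumab without SAR444245. It should settle three items explicitly: which attributions qualify, whether clinical benefit is required and who judges it, and whether the Sponsor must be contacted first. The choice on each item is the sponsor's.

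State the conditions once, and have 6.5.4.4 and the Grade 3 and Grade 4 rows of Table 3 refer to them. When doing so, check that the result agrees with the restart rule in 6.5.2 and with footnote b of Table 5.

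The cost is a few sentences in three places. No analysis, sample size or assessment schedule changes. No change to the consent text is proposed, since none is shown to be needed.
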